3.0 SUBJECT ELIGIBILITY Subject Eligibility

Eligibility waivers are not recommended; however, if warranted, prior approvals are required per Section 11.6.1. Subjects must meet all inclusion and exclusion criteria to be registered to the study. Study treatment may not begin until a subject is registered. Once registered, a subject is still required to meet all inclusion and exclusion criteria on the first day of treatment, prior to treatment.

3.1 Inclusion Criteria

- 3.1.1 Bladder cancer, confirmed pathologically on transurethral resection of bladder tumor (TURBT) or on bladder biopsy. Pure urothelial, variant urothelial, or any proportion of squamous cell carcinoma are permitted. Questions about eligibility may be resolved by consultation with UTSW pathology but formal pathologic review is not required.
- 3.1.2 Bulky, clinically node positive disease (cN+) defined as: 1) a single pelvic lymph node of ≥ 1.5 cm largest diameter on CT or MRI; or 2) multiple pelvic lymph nodes ≥ 1 cm largest diameter on CT or MRI. Pathologic confirmation is not required. Imaging to establish eligibility must have been obtained no more than 60 days prior to trial enrollment. The scans must be personally reviewed by the enrolling clinician. For imaging studies obtained outside of UT Southwestern, imaging review of node status and sign off by the enrolling investigator is required. Review and sign off by a UTSW radiologist is optional in ambiguous or questionable cases, but is not mandatory.
- 3.1.3 Age ≥ 18 years.
- 3.1.4 ECOG performance status 0-1.
- 3.1.5 Appropriate candidate for radical cystectomy, as determined by the treating urologist.
- 3.1.6 Appropriate candidate for stereotactic ablative radiotherapy, as determined by the treating radiation oncologist.
- 3.1.7 Patient is planned to initiate or is within 1-3 weeks of initiation of FDA-approved immune checkpoint inhibitor therapy based on ineligibility to receive platinum-based downstaging chemotherapy (DCT) (Cohort 1, as detailed below) or failure to achieve clinical complete response to platinum-based DCT (Cohort 2, as detailed below).

Cohort 1 (chemotherapy-ineligible) – either of:

- patient staged with bulky cN+ disease as defined above, medically ineligible to receive any platinum-based chemotherapy or, after appropriate and documented counseling, refusing to receive any-platinum-based chemotherapy; *or*
- patient staged with bulky cN+ disease as defined above, medically ineligible to receive cisplatin-based chemotherapy, with PD-L1 positive tumor (according to methodology described in the FDA approval label for the respective ICI agent)

Cohort 2 (chemotherapy non-responding) – any of:

- patient, initially staged with bulky cN+ disease as defined above, with radiologic progression after two cycles of platinum-based DCT (per RECIST 1.1 criteria: $\geq 20\%$ increase in summed short-axis diameter of visible lesions with ≥ 5 mm absolute increase)
- patient, initially staged with bulky cN+ disease as defined above, failing to achieve radiologic complete response after three or four cycles of platinum-based DCT (failure of all enlarged lymph nodes to decrease to < 1 cm short-axis diameter)
- patient, initially staged with bulky cN+ disease as defined above, failing to achieve radiologic complete response after one or two cycles of platinum-based DCT which was discontinued due to patient intolerance
- patient, initially not staged with bulky cN+ disease as defined above, who progresses to cN+ disease as defined above after two or more of cycles of platinum-based DCT

- 3.1.8 Permitted downstaging chemotherapy regimens are gemcitabine/cisplatin (gem/cis), gemcitabine/carboplatin (gem/carbo), and methotrexate/vinblastine/doxorubicin/cisplatin (MVAC, in any dose variant).
- 3.1.9 Permitted immune checkpoint inhibitor agents are those FDA-approved for platinum-ineligible (Cohort 1) or platinum-refractory (Cohort 2) bladder cancer: atezolizumab or pembrolizumab for Cohort 1; avelumab, nivolumab, or pembrolizumab for Cohort 2. If additional immune checkpoint inhibitor (anti-PD1, anti-PD-L1, and/or anti-CTLA4) agents are approved for use in advanced urothelial carcinoma during the study, these agents will be permitted as well.
- 3.1.10 Women of child-bearing potential and men must agree to use adequate contraception (hormonal or barrier method of birth control; abstinence) prior to study entry, for the duration of study participation, and for 90 days following completion of therapy. Should a woman become pregnant or suspect she is pregnant while participating in this study, she should inform her treating physician immediately.

A female of child-bearing potential is any woman (regardless of sexual orientation, having undergone a tubal ligation, or remaining celibate by choice) who meets the following criteria:

- Has not undergone a hysterectomy or bilateral oophorectomy; *or*
- Has not been naturally postmenopausal for at least 12 consecutive months (i.e., has had menses at any time in the preceding 12 consecutive months).

3.1.11 Ability to understand and the willingness to sign a written informed consent.

3.2 Exclusion Criteria

- 3.2.1 Medical or anatomic contraindication to any of the study treatment modalities (radical cystectomy, stereotactic ablative radiotherapy, immune checkpoint inhibitor therapy).
- 3.2.2 Non-urothelial histology (other than pure squamous cell, which is permitted) including pure adenocarcinoma, pure small cell carcinoma, sarcoma, lymphoma, non-genitourinary primary (e.g. colorectal).
- 3.2.3 Metastatic (cM1) disease, defined as 1) lymph nodes ≥ 1 cm above the aortic bifurcation (cM1a), or metastases to bone, brain, or any visceral site (cM1b). Patients with a single enlarged retroperitoneal lymph node will be eligible with an adequately performed lymph node biopsy showing no metastatic disease or with a PET scan showing absence of FDG avidity.
- 3.2.4 Second primary malignancy, except: 1) non-metastatic (cM0) prostate cancer, 2) non-metastatic (cM0) endometrial cancer, 3) non-melanoma skin cancer, 4) cervical squamous cell carcinoma *in situ*, 4) any AJCC Stage I/II or organ-confined primary malignancy for which the patient has undergone curative treatment and has been without evidence of disease for three years.
- 3.2.5 Prior pelvic radiation therapy.
- 3.2.6 Autoimmune disease rendering the patient ineligible for ICI.
- 3.2.7 Treatment with any immunosuppressive agent within 14 days of study entry, excluding topical or inhaled corticosteroids or adrenal-replacement steroids.
- 3.2.8 End stage renal disease requiring dialysis.
- 3.2.9 HIV infection, unless stable on HAART with CD4+ count > 400 .
- 3.2.10 Subjects may not be receiving any other investigational agents for the treatment of the cancer under study.
- 3.2.11 History of allergic reactions attributed to compounds of similar chemical or biologic composition to atezolizumab, avelumab, durvalumab, nivolumab, pembrolizumab, or other agents used in study.
- 3.2.12 Uncontrolled intercurrent illness including, but not limited to, ongoing or active infection, symptomatic congestive heart failure, unstable angina pectoris, cardiac arrhythmia (other than atrial fibrillation / atrial flutter), or psychiatric illness/social situations that, in the opinion of the investigator, would limit compliance with study requirements.
- 3.2.13 Subjects must not be pregnant or nursing due to the potential for congenital abnormalities and the potential of this regimen to harm nursing infants.

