- ability to provide informed consent
- negative pregnancy test (female of child-bearing age)
- agrees to use adequate contraception *or* female not of child-bearing age

EXCLUSION criteria - confirm absence of all of the following:

- pure adenocarcinoma, pure small cell carcinoma, sarcoma, lymphoma, non-genitourinary primary tumor, or other non-urothelial histology except squamous cell carcinoma
- metastatic disease (including lymph nodes ≥ 1 cm above the aortic bifurcation, unless accompanied by a negative lymph node biopsy or negative PET scan)
- second primary malignancy, except (check if applicable):
 - cM0 prostate cancer
 - cM0 endometrial cancer
 - non-melanoma skin cancer
 - cervical squamous cell carcinoma *in situ*
 - any AJCC Stage I/II or organ-confined primary malignancy in remission for ≥ 3 years following curative treatment
- prior pelvic radiation therapy
- autoimmune disease resulting in ineligibility for immune checkpoint inhibitor
- treatment with an immunosuppressive agent within 14 days of study entry, except (check if applicable):
 - topical or inhaled corticosteroids
 - adrenal-replacement steroids

- end-stage renal disease requiring dialysis
- HIV infection, unless stable on HAART with CD4+ count of > 400
- receipt of other investigational agents or treatment modalities
- history of true allergic or anaphylactic reaction to atezolizumab, avelumab, durvalumab, nivolumab, pembrolizumab, or other similar agent
- uncontrolled intercurrent illness including active infection, symptomatic congestive heart failure, unstable angina pectoris, cardiac arrhythmia (other than atrial fibrillation / atrial flutter), or psychiatric illness resulting in inability to safely undergo the study or complete study requirements
- pregnancy or current breastfeeding

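### The prostate and endometrial exceptions in 3.2.4 require cM0 but not cN0, so pelvic nodes from a second cancer could qualify and be counted as bulky bladder cancer

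*Combined protocol and SAP*

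**What the plan says.** Section 3.2.4 opens the list of tolerated second cancers with "non-metastatic (cM0) prostate cancer, 2) non-metastatic (cM0) endometrial cancer". Neither entry carries a condition on nodal stage, treatment or remission. The last entry in the same list is much tighter: it covers "any AJCC Stage I/II or organ-confined primary malignancy for which the patient has undergone curative treatment" and adds three years without evidence of disease. The Appendix A checklist repeats the loose wording, for example "cM0 prostate cancer".

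Section 3.2.3 defines metastatic disease by "lymph nodes ≥ 1 cm above the aortic bifurcation (cM1a), or metastases to bone, brain, or any visceral site (cM1b"). Pelvic nodes are not on that list.

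Section 3.1.2 sets bulky cN+ by size: "a single pelvic lymph node of ≥ 1.5 cm largest diameter on CT or MRI", or multiple pelvic nodes of at least 1 cm. It then states "Pathologic confirmation is not required". The enrolling clinician must review the scans personally, but for the radiologist the text says "Review and sign off by a UTSW radiologist is optional in ambiguous or questionable cases, but is not mandatory".

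The progression definitions (2.4.1 and 6.1.6) and the nodal complete response definition (9.3) do not say which cancer the disease must come from.

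**The concern.** Prostate and endometrial cancers can spread to the same pelvic nodes that define eligibility here. M stage is separate from N stage, so a limit of cM0 leaves node-positive disease inside the exception. A patient with confirmed bladder cancer, a known cN1 cM0 prostate cancer and one 1.5 cm pelvic node passes 3.1.2 and 3.2.4 as written, even if the node belongs to the prostate cancer.

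That patient is outside the population the trial asks about. Three things would follow:

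- The node would be treated and described as bulky cN+ bladder cancer.
- Progression, or its absence, would enter the comparison with the historic 2-year PFS of 30%.
- The node's pathology at cystectomy would enter the nodal response rate.

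**Working it through.** **Reading the criteria together**

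1. Does cM0 imply cN0? Not in this protocol. Section 3.2.3 builds cM1 from nodes above the aortic bifurcation and from bone, brain and visceral sites. A patient with pelvic nodes only is cM0.
2. Does another criterion ask where the nodes come from? Section 3.1.2 and the checklist use size on imaging. Section 3.2.2 concerns the histology of the bladder tumour. Section 3.2.5 removes patients with prior pelvic radiation, but leaves second cancers that are untreated or were treated without it.
3. Does the protocol check nodes elsewhere? Yes. A single enlarged retroperitoneal node needs a negative biopsy or PET (3.2.3). No comparable check applies to pelvic nodes beside a second pelvic cancer.
4. Is there a later correction? Node dissection at cystectomy gives tissue, but only after PULSAR and only in patients who reach surgery. No rule reclassifies a patient whose nodes prove to be from another cancer.

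**The plan's own figure**

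Section 9.2 states 90% power with 24 patients to detect a 27-point rise from 30% (to 57%) at one-sided alpha 0.10. An exact one-sample binomial rule, rejecting at 11 or more of 24 progression-free at two years, gives:

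- P(Bin(24, 0.57) ≥ 11) = 0.904, which matches the stated 90%;
- P(Bin(24, 0.30) ≥ 11) = 0.074, the false-positive rate.

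This rule is a proxy. Section 9.3 plans a log-rank comparison with the historic series.

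**Illustration with one misattributed patient**

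Assumptions: 23 patients have the historic 30% 2-year PFS. One has probability q, which the documents do not give. Then

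P(reject) = P(Bin(23, 0.30) ≥ 11) + q × P(Bin(23, 0.30) = 10) = 0.0546 + q × 0.0655.

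| q | False-positive rate |
|---|---|
| 15% | 6.4% |
| 30% | 7.4% (no change) |
| 50% | 8.7% |
| 60% | 9.4% |
| 80% | 10.7% |
| 100% | 12.0% |

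The rate passes 0.10 when q exceeds (0.10 − 0.0546) / 0.0655 ≈ 0.69.

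**Two or three patients**

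The same exact calculation gives 11.7% for two such patients and 14.5% for three at q = 60%, and 18.6% and 27.7% at q = 100%. At q = 15% it gives 5.6% and 4.8%, below the 7.4% baseline.

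**Primary endpoint**

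Completion is counted by procedures done on time, whatever the origin of the nodes. One patient is 1/27 = 3.7 percentage points of the enrolled total.

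**The case against.** The strongest reply is that an exception in 3.2.4 lifts one exclusion only. Section 4.1 still speaks of clinically node-positive bladder cancer, the checklist asks for clinical concern for node-positive disease, and the treating clinician assigns the nodal stage. A clinician who attributed the nodes to the prostate would probably not stage the bladder cancer as cN+. The word non-metastatic might also be read to bar nodal spread, because the study summary and Section 1.1 call regional nodal disease metastatic.

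Part of this stands: these points make enrolment of such a patient less likely. They do not close the gap. No criterion asks for attribution of the nodes, and the exception is tied expressly to cM0, which 3.2.3 separates from pelvic nodes.

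The objections to size stand in full. A reader might infer that the second cancer inflates PFS and that a single patient breaks the 0.10 level. The documents do not support either inference. The patient still has bladder cancer that is platinum-ineligible, platinum-refused or unresponsive to chemotherapy, and progression of either cancer can count as an event, so a high PFS cannot be presumed. One patient exceeds 0.10 only if q is above about 69%, and only under a rule that is not the planned test. The comparator is the trial-eligible subset of the historic series, and the documents do not say whether that subset contains similar patients. The number affected may be zero.

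**Conclusion.** The point holds as a gap in the eligibility wording. As written, 3.2.4, 3.1.2 and Appendix A admit a patient with a known node-positive prostate or endometrial cancer without asking which cancer the enlarged nodes belong to, and the outcome definitions would then count that disease as bladder cancer disease.

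Its size is unknown and probably small. The frequency of such patients and their PFS are not in the documents, and the direction of bias is open. On the proxy rule, one patient moves the false-positive rate from 7.4% to between 9.4% and 12.0% for q between 60% and 100%, and lowers it for q under 30%. The effect falls on the secondary PFS comparison and the descriptive nodal outcomes. The primary completion endpoint is little affected, and the stated sample size does not change. The reason to act is that the rule admits the wrong population and the correction is cheap. A demonstrated loss of type I error control is not part of the finding.

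**What to change.** - In 3.2.4 and Appendix A, change cM0 to cN0 cM0 for the prostate and endometrial exceptions. Do not add a requirement for organ-confined disease: that would exclude locally extended but node-negative second cancers, which cause no confusion about the nodes.
- In 3.1.2 and Appendix A, state that the enrolling clinician must judge the qualifying pelvic nodes to be from bladder cancer, using imaging and tissue already available, with no new biopsy.

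The cost is a few lines of protocol and checklist text. An occasional patient will be excluded, which matters somewhat when nine patients a year are needed; the documents do not allow an estimate of how many. Attribution will still rest partly on clinical judgement, but the judgement will be required and recorded.

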4.0 TREATMENT PLAN

4.1 PULSAR: Dose and Techniques

Patients are eligible for the trial if they have bulky, clinically node-positive (cN+) bladder cancer and have either recently initiated (within \leq 1 week) or are planned to initiate immune checkpoint inhibitor (ICI) therapy due to either 1) ineligibility for/refusal of platinum-based downstaging chemotherapy; or 2) failure to achieve a complete clinical response to platinum-based downstaging chemotherapy. Patients will initiate PULSAR treatment 1-2 weeks after initiating ICI. PULSAR will be administered in 3 fractions of 12 Gy each (36 Gy total) at 12-16 day intervals and patients will undergo radical cystectomy with bilateral extended pelvic lymph node dissection within 4-8 weeks after completion of PULSAR. ICI therapy will be administered according to the FDA-approved dosing route and schedule and will be continued during PULSAR treatments.

PULSAR treatment will be initiated 1-2 weeks after the patient is initiated on an FDA-approved ICI agent. PULSAR will be administered in 3 fractions of 12 Gy each at 12-16 day intervals. Target areas will include the region of the bladder containing the primary tumor (confirmed, if necessary, on office flexible cystoscopy at UTSW) and to up to five targetable, pathologically enlarged bulky lymph nodes (as deemed feasible by the treating radiation oncologist). Non-enlarged pelvic lymph nodes will be spared to minimize adverse effects on the tumor immune response.

4.1.1 PULSAR will be delivered with the targeting, planning, and directing of treatment fields guided to a target based on known 3D coordinates related to reliable fiducial markers. This differs from conventional radiation therapy in which treatment is guided by skin or bony landmarks assumed to correlate to the target volume based on the initial simulation. Treatment will account for inter/intra-fractional errors with careful dosimetry that delivers an ablative dose to the involved lesions while respecting normal tissue constraints. In the event that fiducial placement is deemed unfeasible or unsafe, or would result in an unacceptable delay in treatment, fiducial placement may be omitted and targeting based on a combination of pre-treatment imaging and findings on flexible cystoscopy.

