HRPP	Human Research Protections Program
ICI	Immune Checkpoint Inhibitor
IDE	Investigational Device Exemption
IHC	Immunohistochemistry
IND	Investigational New Drug
IV (or iv)	Intravenously
MIBC	muscle invasive bladder cancer
MRI	Magnetic Resonance Imaging
MTD	Maximum Tolerated Dose
NACT	Neoadjuvant chemotherapy
NCI	National Cancer Institute
ORR	Overall Response Rate
OS	Overall Survival
PBMCs	Peripheral Blood Mononuclear Cells
pCR	Pathologic Complete Response
PD	Progressive Disease
PET	Positron Emission Tomography
PFS	Progression Free Survival
p.o.	per os/by mouth/orally
PR	Partial Response
PULSAR	Personalized ULtrafractionated Stereotactic Adaptive Radiotherapy

RCB	Residual Cancer Burden
RECIST	Response Evaluation Criteria in Solid Tumors
RFS	Recurrence Free Survival
SAbR	Stereotactic Ablative Radiotherapy
SAE	Serious Adverse Event
SCCC	Simmons Comprehensive Cancer Center
SD	Stable Disease
SGOT	Serum Glutamic Oxaloacetic Transaminase
SoC	Standard of Care
SPGT	Serum Glutamic Pyruvic Transaminase
WBC	White Blood Cells

STUDY SCHEMA

STUDY SUMMARY

Title	Checkpoint Inhibitor and Radiation Therapy in Bulky Node-Positive Bladder Cancer (CIRTiN-BC): A Phase II, Single-Arm Trial
Short Title	CIRTiN-BC
Protocol Number	STU-2021-0114
Phase	Phase I/II
Methodology	Single-arm safety/efficacy trial
Study Duration	36 months
Study Center(s)	Single center at UT Southwestern Medical Center, with potential expansion to Parkland Hospital and John Peter Smith Hospital
Objectives	To evaluate the safety and efficacy of PULSAR in patients with bulky node-positive bladder cancer on immune checkpoint inhibitor therapy due to ineligibility for or failure to respond to downstaging chemotherapy
Number of Subjects	27
Diagnosis and Main Inclusion Criteria	bladder cancer with bulky regional lymph node metastases, planning immune checkpoint inhibitor therapy due to ineligibility for downstaging chemotherapy or failure to respond to downstaging chemotherapy
Study Product(s), Dose, Route, Regimen	PULSAR (personalized ultrafractionated stereotactic ablative radiotherapy) 30 Gy in 3 fractions
Duration of administration	3 fractions at 12 - 16 day intervals
Reference therapy	standard of care with systemic therapy alone, followed by radical cystectomy if treatment response

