4.1.2 Radiation Therapy Prescription Dose

The treating radiation oncologist can choose to deliver 10 or 12 Gy per fraction depending on the clinical circumstances, i.e. anatomical location and adjacent organs-at-risk. Each radiation therapy fraction will encompass the 95% of the planning target volume, and is considered compliant to the protocol. The following table lists the acceptable range of dose per fraction, with preference for the higher dose if safely achievable. Any dose delivered that is beyond the recommended doses will be considered an unacceptable variation.

Number of fractions	Dose per fraction	Total dose
3	10-12 Gy	30-36 Gy

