4.4.2 Target Volumes

The target lesion will be outlined by an appropriately trained physician and designated the gross tumor volume at the primary site (GTVp) and nodal site(s) GTVn. The targets will generally be drawn using appropriate windowing based on location of the primary tumor and metastatic lymph nodes. Given that this treatment will adapt to changes in tumor dimension, the clinical target volume (CTV) will correspond to the GTVp/GTVn with no added margin. A 5 mm planning target volume (PTV) margin will be added to account for setup and internal motion.

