4.5.2 Dose Calculations

For purposes of dose planning and calculation of monitor units for actual treatment, this protocol will require tissue density heterogeneity correction.

Successful treatment planning will require accomplishment of all of the following criteria:

1. Maximum dose: The treatment plan should be created such that 100% corresponds to the maximum dose delivered to the patient. This point must exist within the PTV.
2. Prescription isodose: The prescription isodose surface must be $\geq 60\%$ and $< 90\%$ of the maximum dose.
3. Prescription Isodose Surface Coverage: The prescription isodose surface will be chosen such that 95% of the target volume (PTV) is conformally covered by the prescription isodose surface (PTV V95%RX = 100%) and 99% of the target volume (PTV) receives a minimum of 90% of the prescription dose (PTV V90%RX $> 99\%$).

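### The PULSAR dose is stated three ways, and a 36 Gy plan that section 4.1.2 accepts can also be a major violation of the 33 Gy bladder-wall limit

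*Combined protocol and SAP*

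**What the plan says.** **Dose.** The Study Summary gives the regimen as "30 Gy in 3 fractions". Section 4.1 says "PULSAR will be administered in 3 fractions of 12 Gy each (36 Gy total) at 12-16 day intervals" and repeats 12 Gy per fraction in its next paragraph. Section 4.1.2 lets the radiation oncologist choose 10 or 12 Gy per fraction according to anatomy and nearby organs. It tabulates 30-36 Gy in total, "with preference for the higher dose if safely achievable", and treats doses outside that range as unacceptable. On compliance it says "Each radiation therapy fraction will encompass the 95% of the planning target volume, and is considered compliant to the protocol".

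**Target.** Section 4.1 says "Target areas will include the region of the bladder containing the primary tumor". Section 4.4.2 sets the clinical target volume equal to the gross tumour volume, with no margin, and then says "A 5 mm planning target volume (PTV) margin will be added to account for setup and internal motion".

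**Coverage.** Section 4.5.2, item 3, requires that "95% of the target volume (PTV) is conformally covered by the prescription isodose surface (PTV V95%RX = 100" (the parenthesis closes with a percent sign), and that "99% of the target volume (PTV) receives a minimum of 90% of the prescription dose". Items 1 and 2 put the plan maximum inside the PTV and the prescription isodose at 60% or more, but below 90%, of that maximum.

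**Organ limit.** The three-fraction table in section 4.6.1 is introduced as covering normal tissue. Its bladder-wall row gives less than 15 cc at 17 Gy and a maximum point dose of 33 Gy, a point being 0.035 cc or less. More than 2.5% over a limit is a minor violation, and more than 5% over is a major one. Neither the table nor its footnotes mention wall that lies inside the PTV.

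**The concern.** There are two linked problems. First, the Summary and section 4.1 each give one end of the section 4.1.2 range as though it were fixed, so staff working from different sections can plan different totals. Second, the organ being treated is also an organ with a limit, and the limit lies between the two permitted totals. If wall inside the PTV counts, the dose that section 4.1.2 prefers can breach a limit that section 4.6.1 calls a major violation.

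What is at stake is the definition of the experimental treatment and of an overdose to the treated organ. The radiotherapy quality review in section 4.7 is given no rule for separating intended target dose from excess dose to normal bladder wall. Section 10.5.3 notes that serious noncompliance used to be called major deviations or violations, and requires it to be reported to the IRB within five working days. The label can therefore have a reporting consequence, or be applied differently from case to case.

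**Working it through.** **Inputs.** Dose per fraction 10 or 12 Gy, three fractions (4.1, 4.1.2); bladder-wall point limit 33 Gy, volume limit 15 cc at 17 Gy, violation margins 2.5% and 5% (4.6.1); coverage and isodose rules (4.5.2).

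**1. The stated totals reproduce.** 3 × 10 = 30 Gy (Summary) and 3 × 12 = 36 Gy (4.1). Difference: 36 − 30 = 6 Gy; 6/30 = 20%.

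**2. Violation thresholds.** Minor: 33 × 1.025 = 33.825 Gy. Major: 33 × 1.05 = 34.65 Gy.

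**3. Prescription against the limit.**

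| Prescription | Ratio to 33 Gy | Wall in the PTV receiving exactly that dose |
|---|---|---|
| 30 Gy | 30/33 = 0.909 (9.1% under) | within the point limit |
| 36 Gy | 36/33 = 1.091 (9.1% over) | beyond 34.65 Gy: major violation, if the row applies |

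**4. Does the coverage rule give a way out at 36 Gy?** Section 4.5.2 can be read in two ways.

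- *By its words:* 95% of the PTV gets 36 Gy and 99% gets at least 0.90 × 36 = 32.4 Gy. Up to 5% of the PTV may fall below prescription, but all except 1% must still reach 32.4 Gy. Wall in that portion has 33.0 − 32.4 = 0.6 Gy in which to meet the limit, and 34.65 − 32.4 = 2.25 Gy in which to avoid a major violation.
- *By the parenthesis*, taking V95%RX = 100% to mean that all of the PTV gets at least 95% of prescription: every part gets at least 0.95 × 36 = 34.2 Gy, and 34.2/33 = 1.036. Any wall in the PTV larger than a 0.035 cc point, if not exempt, is then at least a minor violation.

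The same tissue can therefore be classed differently depending on which half of one sentence is used.

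**5. Hot spots.** Plan maximum = prescription ÷ isodose fraction. At 36 Gy: above 36/0.90 = 40 Gy and up to 36/0.60 = 60 Gy. At 30 Gy: above 30/0.90 = 33.3 Gy and up to 30/0.60 = 50 Gy, passing 34.65 Gy once the prescription isodose is below 30/34.65 = 86.6% of maximum. These maxima count against the row only if the hot spot lies in bladder wall.

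**6. Volume limit.** 99% of the PTV gets at least 0.90 × 30 = 27 Gy or 0.90 × 36 = 32.4 Gy, both above 17 Gy. At either dose, nearly all wall in the PTV counts towards the 15 cc unless it is exempt. Whether 15 cc is exceeded depends on wall volumes that the documents do not give.

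**The case against.** The strongest reply has four parts.

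- *Section 4.1.2 governs the dose.* It covers both totals, so a planner following the Summary or section 4.1 stays within the accepted range. This is true and narrows the first problem to unharmonised text. It does not remove it: section 4.1 is in the treatment plan itself and states 36 Gy without qualification.
- *The higher dose is conditional.* Section 4.1.2 makes the choice depend on organs at risk and on safety, and section 4.1.1 says planning respects normal-tissue constraints. But the bladder-wall row is one of the tests of those conditions, and its scope is undefined, so the conditions cannot settle the question.
- *The table covers normal tissue only.* Together with the mention of involved lesions in section 4.1.1, this is a fair basis for leaving tumour-bearing wall out of the row. It does not deal with uninvolved wall in the 5 mm margin, which is outside the tumour volume as defined but inside the volume to be covered.
- *Coverage and organ limits are separate tests.* Passing one and failing the other is normally no contradiction. Here the target lies within the constrained organ, so meeting the coverage rule can itself cause the breach.

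Some points stand. The parenthesis in section 4.5.2 may be only a slip of notation. Section 10.5.3 defines serious noncompliance by its effect on risk, rights or data, so a major violation under section 4.6.1 is not automatically reportable. No breach has been shown to be unavoidable.

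**Conclusion.** The concern holds. The dose statements disagree by up to 6 Gy (20%). At 36 Gy, bladder wall that counts under section 4.6.1, stays in the PTV for all three fractions and receives the prescription dose is 9.1% over the 33 Gy limit. That is past the 5% major-violation line, in a plan that section 4.1.2 treats as compliant.

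This is a possibility under the rules as written, not a certainty for each plan. It is avoided if wall inside the PTV is read as exempt, if the adapted PTV leaves that wall out of later fractions, or if the wall falls in the small part of the PTV allowed below prescription. At 30 Gy the prescription itself is under the point limit, but the hot-spot and 15 cc questions remain open. Sample size, the primary endpoint and the progression-free survival analyses do not depend on any of this.

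**What to change.** Amend the wording in three places:

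1. Reconcile the Study Summary, section 4.1 and section 4.1.2 into one consistent dose statement.
2. In section 4.6.1, state which bladder wall, relative to the primary-site PTV, the row applies to. Cover the point limit, the 15 cc limit and the minor and major thresholds.
3. In section 4.5.2, item 3, make the sentence and its parenthesis state the same coverage requirement, and check the result against the bladder-wall row.

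The clinical team should set the dose, the limits and the scope of the row; this review takes no view on them. The cost is a protocol wording amendment, with no extra patients or procedures.
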